Document History – Changes compared to previous version of RAP module 3 (Final Draft version 1.0, October 16, 2013).

Version	Date of change	Page	Changes
Final version 2.0 (Amendment 1 to Final Draft 1.0, dated Oct 16, 2013)	9/15/2016	7	(Analysis sets) Several items in exclusions from analysis sets due to PDs have been changed due to the changes in the PD list and the reconsideration of the analysis sets.
		10	(Subgroup analyses) Subgroup defined by the randomization baseline eGFR values and NYHA classifications are added; Definition of regions has been changed according to the countries involved in the study.
		12	Baseline for biomarkers has been corrected to visit 101/102. MMSE has been added to the list to be collected at randomization baseline. Analysis cut-off date has been updated for the new sample size.
		10	South Africa and Israel have been moved to Asia/Pacific and other under the new definition of region. Slovenia is added to Central Europe. Countries not participating the study are removed.
		15, 16, & 21	The ACEi intolerant subgroup summary for background and demographic characteristics has been removed. Baseline LVEF <= median subgroup summary has been added.
		17 to 19	The exposure duration calculation formulas for the dose level 2 in sub-run-in phase have been corrected. The dose level 3 was erroneously included in the calculation for the run-in and has been removed. More exposure duration analyses for dose down- and up-titration are added.
		20	Formula of “Daily dose for each patient” are updated to reflect BID.
		24 to 26	Secondary analysis (based on the protocol amendment 2): (1) The extended composite endpoint variable (CV death, total HF hospitalizations, total non-fatal strokes, and total non-fatal MIs) and time to new onset Atrial fib are moved to the exploratory analysis from the secondary analysis; KCCQ clinical summary score at month 8 and time to 1 st composite renal impairment endpoint have been added to the secondary analysis. In total we still have four secondary endpoints. Exploratory analysis: (2) The extended composite endpoint variable is added; (3) Number of worsening HF events or CV death per-subject has been replaced by number of total worsening HF events and CV death per-subject. The definition of worsening HF event is given; (4) Number of days alive and out of hospital (DAOOH) during the randomized, double-blind study period and percentage of DAOOH over potential follow-up time is added;

Version	Date of change	Page	Changes
			
(5) Time to 1st occurrence of composite renal impairment event is removed;
 
(6) Time to new onset AF is moved here;
 
(7) Number of ICU stays is added;
 
(8) Cardiac related biomarkers are added to the analysis list;
 
(9) Change from baseline in MMSE summary score at year 2 (week 96) is added;
 
(10) Indicator of presence of AF >5 minutes (for the AF substudy) is removed;
 
(11) AF burden measured by the total AF duration over total monitoring time is removed
 
(12) Echocardiographic parameters (in a subset of patients) are removed.

		27	The 0.02499 in “The primary hypothesis will be tested at a one-sided significance level of 0.02499 adjusted for the interim analysis.” has been corrected to 0.024. Nelsen-Aalen estimate has been moved to Page 30.
		27	In the primary analysis model, “ties = breslow” has been changed to “ties = efron” as requested by the FDA. The general baseline rate and hazard functions are changed to constant baseline rate and hazard in the joint shared frailty model, to simplify the modeling based on the experience from PARADIGM-HF. Piecewise constant baseline rate and hazard functions will be used for the sensitivity analysis. The BIC criterion will be used to select the number of pieces. The marginal time-to-CV death analysis has been added to use Cox’s regression analysis. The following sentence “The inference on the total HF hospitalizations can only be made when both the composite endpoint and the total HF hospitalizations itself showed statistically positive results” has been removed in order to reduce the confusion about how to make the primary inference.
		31	A new supportive analysis of performing the LWYY model on HF hospitalizations alone has been added. A pooled-weighted effect size from this analysis and the Cox’s regression analysis on CV death has also been added.
		32	R codes for multi-state model have been modified. On-treatment LWYY analysis is added as supportive analysis to the primary efficacy.
		33 to 35	Due to the change in the secondary objectives, the endpoints and the testing scheme in the multiple hypotheses testing procedure for the secondary efficacy analysis have been changed accordingly.
		35 to 36	The analysis specifications for the KCCQ CSS (mean change and responder analyses) at Month 8 have been added. The analysis for composite renal impairment has been added. The analyses for the extended composite endpoint and new onset AF have been removed from secondary analyses. Missing NYHA class change due to death will be imputed as worsened.

Version	Date of change	Page	Changes
		37 to 43	
For the exploratory analyses, the following analyses are updated according to protocol amendment (PA) 2:
 
 1. Time to new onset AF; 2. Time-to-recurrent-composite event of CV death, total HF hospitalizations, total strokes, and total MIs; 3. Analyses for changes in health-related quality of life change (KCCQ scores and EQ-5D); 4. Analysis for rate of change in eGFR; 5. Analysis of biomarkers; 6. Analysis of days alive out of hospital; 7. Analysis of MMSE; 8. Analysis of count data. 
The details for the analysis for MMSE are added. The subgroup analysis for MMSE is also specified.

		39 to 45	
Analysis related to pharmacokinetics parameters are added. In Table 10-2:
 
 1. Hyperkalemia related AE by baseline hyperkalemia status is removed. 2. Symptomatic hypotension related are removed. 3. Cutoff for SBP is updated to 100 from 90 mmHg. 4. Risks deleted: gastric lesions, stimulation of lipolysis, QT-prolongation. 5. Risks added: embryo-fetal toxicity/lethality, neonatal/infantile toxicity, statin drug-drug interaction.
		47	
Analysis for cognitive impairment has been explicitly listed in the analysis for change in cognitive function.

		50 to 51	
For interim analysis, the following modifications have been made according to the protocol amendments (PA) 2 and 3.
 
 1. Move the interim efficacy analysis to occur after approximately two-thirds of the target number of primary composite events (i.e., ~1231 primary composite events) rather than half as previously defined; (PA 2) 2. Eliminate the futility analysis; (PA 2) 3. The statistical stopping rules for superiority of LCZ696 over valsartan is modified from one-sided p-value of <0.0001 for the primary endpoint to one-sided p-value of <0.001 for both the primary endpoint and CV death at the interim efficacy analysis. (PA 3)

Version	Date of change	Page	Changes
		51, 52	According to the protocol amendment 3, the total sample size has been readjusted from 4300 to 4600 to increase the statistical power from 81% to close to 85% to detect a 25% reduction in recurrent heart failure hospitalizations. The sample size re-estimation was based on a recent analysis on recurrent heart failure hospitalization in the PARADIGM-HF, which showed that LCZ696 resulted in approximately a 25% reduction in recurrent heart failure hospitalizations relative to enalapril. The target number of primary events is also increased to 1847, which corresponds to conducting the interim efficacy analysis when ~1231 primary composite events have been confirmed by adjudication. As described in Table 13-1, a 25% reduction in recurrent heart failure hospitalizations is expected to correspond to an overall 19% reduction in the primary endpoint (CV deaths and total recurrent heart failure hospitalization).
		53, 54	For the secondary endpoints, the powers are also updated according to the new sample size.
		54	Reference of Andersen and Gill (1982) is added.
Amendment of final version 2.0 (Amendment 2 to Final Draft 1.0, dated Oct 16, 2013)	8/1/2018	10	Slovenia is added to Central Europe. Countries not participating the study are removed.
		20	Formula of "Daily dose for each patient" are updated to reflect BID.
		32	On-treatment LWYY analysis is added as supportive analysis to the primary efficacy.
		39	Analyses related to pharmacokinetics parameters are added.
		45	In Table 10-2: 
 1. Hyperkalemia related AE by baseline hyperkalemia status is removed. 2. Symptomatic hypotension related are removed. 3. Cutoff for SBP is updated to 100 from 90 mmHg. 4. Risks deleted: gastric lesions, stimulation of lipolysis, QT-prolongation. 5. Risks added: embryo-fetal toxicity/lethality, neonatal/infantile toxicity, statin drug-drug interaction.

Version	Date of change	Page	Changes
Amendment 3 (Amendment 3 to Final Draft 1.0, dated Oct 16, 2013)	5/28/2019	10	(Table 2-1) Protocol deviations leading to exclusion from analysis sets are updated. Removed: 
 History of severe pulmonary disease (exclusion criteria); LVEF \geq45% not measured by echocardiogram (echo) during the screening epoch, or within 6 months prior to Visit 1 (inclusion criteria); Lack of evidence for left atrial (LA) enlargement or left ventricular hypertrophy (LVH) as defined by the protocol (inclusion criteria). Added: 
 Most recent LVEF measured $<$45 by ECHO, or LVEF % not measured; NYHA class I Visit 1.
		11	(Subgroup analyses) Subgroup of atrial fibrillation based on history prior to randomization is added in addition to the existing atrial fibrillation based on ECG at randomization.
		14	Analysis cut-off date information is added.
		32	Analysis of time to first primary composite event (CV death or hospitalization for HF) was added as supportive analysis to the primary efficacy objective. Analysis includes: 
 Cox proportional hazards model; Additionally, Log-rank test will be performed.
		34	CV death component in primary LWYY analysis is replaced with the following as supportive analyses to the primary efficacy objective: 
 Death due to CV or unknown cause; All-cause death. Time-dependent systolic blood pressure (SBP) covariate adjusted LWYY and Cox analyses are added as supportive analyses to the primary efficacy objective.
		39	Component analysis (joint frailty model) for item 2 is removed.
		41	Pharmacokinetics related analyses will be presented in a separate report.
		42	The subgroup analysis for MMSE is specified with more interaction terms.
		48	In Table 10-2: 
 Risks deleted: change in bone growth/bone mineral density. Risks updated or added: neonatal/infantile toxicity through exposure from breast milk, anaphylaxis/anaphylactoid reactions, malignancy.
		55	Table 13-1: one typo is corrected.
		#	Besides the above noted changes, some minor edits to the text are also made to correct some words or order of texts.

Statistical and analytical plans

1 Introduction

Data will be analyzed according to the data analysis section 10 of the study protocol which is available in Appendix 16.1.1 of the CSR. Important information is given in the following sections and details are provided, as applicable, in Appendix 16.1.9 of the CSR.

2 Analysis set

The following analysis populations will be defined for statistical analysis:

- **Screened set (SCR)** – All patients who signed the informed consent. The *screened set* includes only *unique screened patients*, i.e., in the case of *re-screened patients* only the chronologically last screening data is counted.
- **Enrolled set (ENR) (run-in phase)** – All patients who received at least one dose of run-in study drug.
- **Valsartan run-in set (VRS)** – All patients who are in the ENR and received at least one dose of run-in valsartan.
- **LCZ696 run-in set (LRS)** – All patients who are in the ENR and received at least one dose of run-in LCZ696.
- **Randomized set (RAN)** – All patients who received a randomization number, regardless of receiving trial medication.
- **Full analysis set (FAS)** – All randomized patients. This is the primary efficacy population applied in efficacy analyses for all efficacy endpoints. Following the intent-to-treat principle, patients are analyzed according to the treatment they have been assigned to at randomization. However, patients who did not qualify for randomization but were inadvertently randomized into the study and did not receive study medication may be excluded from FAS. Further exclusions from the FAS may only be justified in exceptional circumstances (e.g., *serious* GCP violations). These potential incidences imply the possibility that the FAS may be smaller than the RAN.
- **Per protocol set (PPS)** – A subset of the FAS, consists of all randomized patients in FAS who received at least one dose of study drug during the double blind period of the study and have no major protocol deviations. Major protocol deviations are those affecting the primary endpoint analyses, which will be identified prior to the final database lock.
- **Safety set (SAF)** – All randomized patients who received at least one dose of study drug during the double blind period of the study. Patients will be analyzed according to treatment received. Treatment received will be considered identical to the randomized treatment if the patient has received at least one dose of the randomized treatment.

The following [Table 2-1](#) contains a sample of current study specific important protocol deviations that lead to exclusion from analysis sets in the study. The final list may be different from this and will be signed before DBL.

Table 2-1 Specification of protocol deviations which lead to exclusion from analysis sets

Category	Description of Protocol Deviation	Inclusion / Exclusion in analyses	Identification method	Person responsible for identification
General	GCP issue present at site	Excluded from PPS,FAS	Manual	Field monitor (FM)
	Blind broken locally	Excluded from PPS	Manual	FM
	Informed consent missing	Excluded from PPS, FAS, SAF, RAN	Manual	FM
Study treatment	Patient randomized but no study medication taken.	Excluded from SAF	Programmable	TDM
	Patient was mis-randomized (patient randomized in error and no DB study medication taken).	Excluded from PPS, FAS, SAF	Manual	FM
Exclusion criteria	History of dilated cardiomyopathy, including peripartum cardiomyopathy, chemotherapy induced cardiomyopathy, or viral myocarditis.	Excluded from PPS	Manual	FM
	Heart transplant or ventricular assistance device (VAD) or intent to transplant (on transplant list) or implant a VAD	Excluded from PPS	Manual	FM
Inclusion criteria	NYHA class I at Visit 1	Excluded from PPS	Programmable	TDM
	Most recent LVEF measured <45 by ECHO, or LVEF % measured by non-ECHO methods	Excluded from PPS	Manual	FM
	Lack of 1) HF hospitalization (defined as HF as the major reason for hospitalization or treatment for HF lasting ≥12 hours and including intravenous [IV] diuretics at a healthcare facility) within 9 months prior to Visit 1, OR 2) lack of elevated NT-	Excluded from PPS	Manual	FM

Category	Description of Protocol Deviation	Inclusion / Exclusion in analyses	Identification method	Person responsible for identification
	proBNP > 300 pg/ml for patient not in AF on Visit 1 ECG or > 900 pg/ ml for patient in AF on Visit 1 ECG			

3 Subgroup definitions and subgroup analyses

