	
 2. ≥ 50 years of age, male or female 3. LVEF $\geq 45\%$ by echocardiogram (echo) during the screening epoch, or within 6 months prior to Visit 1 (any local LVEF measurement made using echo only) 4. Symptom(s) of HF requiring treatment with diuretic(s) for at least 30 days prior to Visit 1 5. Current symptom(s) of HF (NYHA Class II-IV) at Visit 1 6. Structural heart disease evidenced by at least one of the following echo findings (any local measurement made during the screening epoch or within the 6 months prior to Visit 1): 
 a. left atrial (LA) enlargement defined by at least one of the following: LA width (diameter) ≥ 3.8 cm or LA length ≥ 5.0 cm or LA area ≥ 20 cm² or LA volume ≥ 55 mL or LA volume index ≥ 29 mL/m² b. left ventricular hypertrophy (LVH) defined by septal thickness or posterior wall thickness ≥ 1.1 cm 7. Patients with at least one of the following: 
 a. a HF hospitalization (defined as HF as the major reason for hospitalization) within 9 months prior to Visit 1 and NT-proBNP >200 pg/ml for patients not in atrial fibrillation/flutter (AF) or >600 pg/ml for patients in AF on Visit 1 ECG, OR b. NT-proBNP >300 pg/ml for patients not in AF or >900 pg/ml for patients in AF on the Visit 1 ECG.

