3.1 Study design

[figure not shown]
Figure 3-1 Study design

This study is a multi-center, randomized, double-blind, parallel group, active comparator, morbidity and mortality trial designed to evaluate the efficacy and safety of LCZ696 compared to valsartan in HF patients (NYHA class II-IV) with preserved EF (Figure 3-1). The study population will consist of patients ≥ 50 years of age with a LVEF $\geq 45\%$ and evidence of structural heart disease (left atrial enlargement [LAE] or left ventricular hypertrophy [LVH]) within 6 months prior to enrollment, current symptomatic HF (NYHA class II-IV) and symptoms of HF requiring treatment with diuretic therapy for at least 30 days prior to Visit 1. In addition, patients will have at least one of the following: (1) a hospitalization for HF within 9 months prior to enrollment and NT-proBNP >200 pg/ml for patients not in AF or >600 pg/ml for patients in AF at Visit 1, **OR** (2) NT-proBNP >300 pg/ml for patients not in AF or >900 pg/ml for patients in AF at Visit 1 (Figure 3-2).

Figure 3-2 Abbreviated inclusion criteria

1. ≥ 50 years of age and LVEF $\geq 45\%$
2. Symptom(s) of HF requiring treatment with diuretic(s) for at least 30 prior to Visit 1
3. Current symptomatic HF (NYHA class II-IV)
4. Structural heart disease (LAE or LVH)

LVEF = left ventricular ejection fraction; HF = heart failure; NYHA = New York Heart Association; LAE = left atrial enlargement; LVH = left ventricular hypertrophy; AF = atrial fibrillation/flutter

Complete inclusion criteria, including diagnostic criteria, are available in Section 4.1.

Patients with documented AF on the Visit 1 ECG will be limited to approximately 33% of the overall study population.

Patients should be on an optimal medical regimen of diuretics and background medications to effectively treat co-morbidities such as HTN, DM, AF and coronary artery disease. Investigators should make every effort to control a patient's BP in accordance with local treatment guidelines and investigator judgment (see Section 5.5.7)

Screening epoch

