3.2 Rationale of study design

3.2.1 Target study population and rationale

The study population will consist of patients ≥ 50 years of age with a LVEF $\geq 45\%$ and evidence of structural heart disease (LAE or LVH), current symptoms of HF (NYHA class II-IV) and prior symptoms of HF requiring treatment with diuretic therapy. In addition, patients will have at least one of the following: (1) a hospitalization for HF within 9 months prior to enrollment and NT-proBNP >200 pg/ml for patients without AF or >600 pg/ml for patients with AF on Visit 1 ECG; **OR**, (2) NT-proBNP >300 pg/ml for patients not in AF or >900 pg/ml for patients in AF on Visit 1 ECG. These criteria should identify the target HFpEF population at risk for major CV events.

Structural heart disease (LAE and LVH) is a key diagnostic criterion for HFpEF in the most recent guidelines ([McMurray et al 2012](#)). Left atrial (LA) size (an integrative measure of left ventricular diastolic pressure) is independently associated with an increased risk of morbidity and mortality ([Zile et al 2011](#)). Including either LAE or LVH will help ensure a diagnosis of HFpEF. The EF lower boundary at 45% was selected to include a wide spectrum of patients for whom no proven therapy is currently available. Prior HF hospitalization and elevated NT-proBNP were the strongest independent predictors of mortality and subsequent HF hospitalization in the I-PRESERVE study ([Solomon et al 2007](#), [Komajada et al, 2011](#)). Patients with baseline AF are required to have higher NT-proBNP levels, as AF is strongly associated with higher levels of NT-proBNP ([McKelvie et al 2010](#)). The number of AF patients will be limited to approximately one third in the current study (based on the Visit 1 ECG) so that the proportion of patients with AF in the study will be representative of the HFpEF population ([Massie et al 2008](#), [Steinberg et al 2012](#), [West et al 2011](#)).

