4.1 Inclusion criteria

Patients eligible for inclusion in this study have to fulfill **all** of the following criteria:

1. Written informed consent must be obtained before any assessment is performed.
2. ≥ 50 years of age, male or female.
3. LVEF $\geq 45\%$ by echo during the screening epoch, or within 6 months prior to Visit 1 (any local LVEF measurement made using echo only).
4. Symptom(s) of HF requiring treatment with diuretic(s) for at least 30 days prior to Visit 1.
5. Current symptom(s) of HF (NYHA class II-IV) at Visit 1.
6. Structural heart disease evidenced by at least one of the following echo findings (any local measurement made during the screening epoch or within the 6 months prior to Visit 1):

- a. left atrial (LA) enlargement defined by at least one of the following: LA width (diameter) ≥ 3.8 cm **or** LA length ≥ 5.0 cm **or** LA area ≥ 20 cm² or LA volume ≥ 55 mL **or** LA volume index ≥ 29 mL/m²
 - b. left ventricular hypertrophy (LVH) defined by septal thickness or posterior wall thickness ≥ 1.1 cm
7. Patients with at least one of the following:
- a. a HF hospitalization (defined as HF as the major reason for hospitalization) within 9 months prior to Visit 1 **and** NT-proBNP >200 pg/ml for patients not in AF or >600 pg/ml for patients in AF on Visit 1 ECG, **OR**
 - b. NT-proBNP >300 pg/ml for patients not in AF or >900 pg/ml for patients in AF on the Visit 1 ECG.

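### The per-protocol exclusion row for prior HF hospitalisation and NT-proBNP does not match inclusion criterion 7: it drops the 7a NT-proBNP floor and widens what counts as a hospitalisation

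*SAP*

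**What the plan says.** Protocol 4.1, inclusion criterion 7, gives two routes into the trial.

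- **Route 7a** is a recent HF hospitalisation joined by 'and' to an NT-proBNP floor. The synopsis has the same text: "a HF hospitalization (defined as HF as the major reason for hospitalization) within 9 months prior to Visit 1 and NT-proBNP >200 pg/ml", with 600 pg/ml as the floor in AF. In section 4.1 the floor reads "NT-proBNP >200 pg/ml for patients not in AF or >600 pg/ml for patients in AF on Visit 1 ECG".
- **Route 7b** is NT-proBNP alone: "NT-proBNP >300 pg/ml for patients not in AF or >900 pg/ml for patients in AF on the Visit 1 ECG".

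The floor on 7a is repeated in section 3.1 ("a hospitalization for HF within 9 months prior to enrollment and NT-proBNP >200 pg/ml for patients not in AF or >600 pg/ml" in AF) and in section 3.2.1 ("NT-proBNP >200 pg/ml for patients without AF or >600 pg/ml for patients with AF on Visit 1 ECG").

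SAP section 2, Table 2-1, has one row for this criterion, with exclusion from the PPS as the consequence and manual identification by the field monitor. The row asks for lack of an HF hospitalisation, and it extends that term to "treatment for HF lasting ≥12 hours and including intravenous [IV] diuretics at a healthcare facility". It then continues "a healthcare facility) within 9 months prior to Visit 1, OR 2) lack of elevated NT"-proBNP above 300 pg/ml, or 900 in AF. Neither 200 nor 600 pg/ml appears in it. The lead-in to the table describes the list as a sample: "The final list may be different from this and will be signed before DBL".

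**The concern.** A row that excludes patients for failing an entry criterion should describe that criterion. This one departs from it in two ways: the hospitalisation limb has no NT-proBNP floor, and it admits a 12-hour IV-diuretic episode that none of the protocol's four statements of 7a contains. The way the row joins its two 'lack of' limbs with OR is also ambiguous. Nothing in either document says that these differences are intended.

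SAP section 9.3.1.2 uses the PPS for supportive runs of the LWYY model and the joint frailty model. If the row is applied as written, those runs can keep patients who did not meet criterion 7 or, on the other reading, lose patients who did. Because the row is applied by hand, different monitors could also read it differently.

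**Working it through.** The plan gives no figure to reproduce, so the check compares the two rules on every type of patient they distinguish.

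**Inputs.** HF history in the 9 months before Visit 1 takes three values: an admission mainly for HF; only a 12-hour IV-diuretic episode; neither. NT-proBNP takes three bands (AF values in brackets): low, up to 200 (600); mid, above 200 to 300 (above 600 to 900); high, above 300 (900). That gives 3 × 3 = 9 profiles.

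**Rules.**

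- Criterion 7, current text: eligible if (admission and not low) or high.
- Table 2-1, reading A (excluded only if both limbs are lacking): kept if admission, or 12-hour episode, or high.
- Table 2-1, reading B (literal, excluded if either limb is lacking): kept if (admission or 12-hour episode) and high.

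| HF history | NT-proBNP | Eligible under criterion 7 | Reading A | Reading B |
|---|---|---|---|---|
| Admission | low | no | **kept** | dropped |
| Admission | mid | yes | kept | **dropped** |
| Admission | high | yes | kept | kept |
| 12-hour episode only | low | no | **kept** | dropped |
| 12-hour episode only | mid | no | **kept** | dropped |
| 12-hour episode only | high | yes | kept | kept |
| Neither | low | no | dropped | dropped |
| Neither | mid | no | dropped | dropped |
| Neither | high | yes | kept | **dropped** |

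Bold marks disagreement with criterion 7.

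**Reading A** disagrees in 3 of 9 profiles, all of them ineligible patients kept. Admission/low comes from the missing floor alone. 12-hour/mid comes from the wider definition alone. 12-hour/low is kept because both departures are present; correcting either one would remove it. No eligible profile is dropped.

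**Reading B** disagrees in 2 of 9 profiles, both eligible patients dropped: those admitted with a mid value (7a), and those with a high value and no HF hospitalisation or 12-hour episode (7b). Protocol 8.6 treats enrolment on NT-proBNP alone as a recognised route, so this reading is unlikely to be meant.

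**Earlier protocol versions.** The protocol's summary of previous amendments says that Amendment 2 changed several entry criteria, without giving the earlier text of this one. Two assumptions cover the range for patients enrolled under an earlier version, on reading A:

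- If the 12-hour episode counted and the floor applied, 12-hour/mid becomes eligible, so 3 − 1 = 2 ineligible profiles are kept.
- If the 12-hour episode counted and there was no floor, admission/low and 12-hour/low become eligible as well, so 2 − 2 = 0 are kept.

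**After the fix.** If the row is written as the negation of criterion 7, all 9 profiles agree with the current protocol.

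**The case against.** The strongest reply is that Table 2-1 is not the operative list. It calls itself a sample, and the signed list is still to come. The SAP also confines PPS exclusions to major deviations that affect the primary endpoint analyses, so it never promised to remove every eligibility failure. Amendment 3 took out the LA enlargement/LVH row and the severe pulmonary disease row, which suggests deliberate narrowing. On that view, a row catching only patients with neither a recent HF hospitalisation nor a raised NT-proBNP is a reasonable choice, and a wide row avoids penalising patients who were eligible under an earlier version. The 12-hour wording may simply spell out what counts as a hospitalisation, a point on which 7a is silent. Upstream controls also limit the numbers: Visit 1 NT-proBNP is measured centrally and reported to the investigator, who must confirm eligibility before randomisation.

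Much of this stands as a limit on weight. The list is open, the PPS is supportive, the literal reading is improbable, the patient count is unknown, and two of the three profiles depend on how the 12-hour episode is regarded. None of it makes the row correct. The sponsor chose to list this criterion and then described a different one, without a version qualifier and without saying that a looser standard was wanted. Amendment 3 revised the table on 28 May 2019, and the row in the amended table still differs from criterion 7. The admission-below-floor profile does not depend on the 12-hour question at all.

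**Conclusion.** The concern holds and is minor. Under the current protocol text, the sensible reading of the row leaves three ineligible profiles of nine in the PPS, and the literal reading removes two eligible ones; neither reproduces criterion 7. The textual mismatch is certain. How many patients it touches cannot be calculated, because the documents give no counts by entry route, and the nine profiles are unweighted. The count of three assumes enrolment under the current criteria; it becomes two or zero under the assumed earlier wordings. The consequence is confined to the supportive PPS analyses.

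**What to change.** Before the deviation list is signed and treatment codes are unblinded, replace the row with the negation of criterion 7, for example: *Meets neither 7a (HF hospitalisation within 9 months before Visit 1, with NT-proBNP >200 pg/ml, or >600 pg/ml if in AF on the Visit 1 ECG) nor 7b (NT-proBNP >300 pg/ml, or >900 pg/ml if in AF on the Visit 1 ECG).* Add that the hospitalisation definition and thresholds are those of the protocol version in force when the patient enrolled. If the missing floor or the 12-hour wording is intended, say so in the SAP and give the reason.

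The text change is one row in a list that the SAP still treats as open. No new data are needed for the floor: Visit 1 NT-proBNP is measured centrally in all patients and a Visit 1 ECG is already scheduled. Applying the version in force takes more work, since amendments take effect only after local ethics approval and about 800 centres are planned. That effort is needed only for patients whose classification differs between versions.
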